4.3 PHARMACOKINETIC VARIABLES

Pharmacokinetics will be measured via serum levels of ABX464 and will be assessed by Abivax. The methods for their analysis are not included in this SAP.

4.4 SAFETY VARIABLES

Safety will be evaluated by the following:

- Adverse events
- Laboratory parameters
- Vital signs (body temperature, systolic and diastolic blood pressure, heart rate)
- Physical examination
- 12-Lead Electrocardiogram (ECG)

5 DEFINITIONS

Study Drug: Study drug is taken to mean either ABX464 or placebo.

Baseline: Baseline is defined by patient and by variable as the last non-missing value before the first dose of study drug.

Study Day: Study day is the number of days since start of treatment where the date of first dose is counted as Day 0.

Protocol Deviation: A deviation related to study inclusion or exclusion criteria, conduct of the trial, patient management or patient assessment. This refers to any change, divergence, or departure from the study design or procedures defined in the protocol. Deviations recorded by the Project Manager or

clinical research associate (CRA), or detected by data management or by statistical programming checks will be reviewed and classed as major or minor during the blind Data Review Meeting (DRM) before database lock (DBL).

Major protocol deviations: These are defined as deviations liable to bias the evaluation of the main efficacy endpoint. The following deviations will be considered as major (non-exhaustive list):

- Non-compliance with the inclusion or exclusion criteria;
- Non-compliance with the study treatment;
- · Intake of prohibited medication;
- Non-compliance with time window.

6 ANALYSIS SETS

Membership of the analysis sets will be reviewed and agreed at a DRM before DBL.

6.1 FULL ANALYSIS SET

The Full Analysis Set (FAS) is defined as those patients who have received at least one dose of the study treatment, and who have at least one baseline value.

The FAS will be used for primary analyses. Patients who receive the wrong treatment in error will be analysed as randomised for efficacy analyses.

6.2 SAFETY SET

The Safety Set is defined as all patients who receive at least one dose of study treatment.

The Safety Set will be used for all safety analyses. Patients who receive the wrong treatment in error will be analysed as treated for safety analyses.

6.3 PER PROTOCOL SET

The Per Protocol (PP) set is defined as those patients of the FAS population without any major protocol deviation and who completed the study (D56).

The PP set will be used for all efficacy analyses.

7 SAFETY MONITORING

No safety monitoring reports are planned.

8 INTERIM ANALYSES

No interim analysis is planned.

9 DATA

9.1 ECRF DATA

eCRF data will be provided by Orion data management to the statistics department as SAS data sets in Orion standard format which will be used for programming the outputs to be included in the clinical study report (CSR). Populated data sets will be available when programming starts. These may contain dummy data if real data is not yet available.

9.2 EXTERNAL DATA

Laboratory parameters, pharmacokinetics, miRNA determination and biopsies will be analysed by central laboratories. Laboratory parameters will be sent to Orion by the Eurofins Central Laboratory, The Netherlands.

No other external data will be received by Orion.

9.3 RANDOMISATION LIST

The randomisation list will be uploaded to a SAS dataset following database lock.

9.4 PROGRAMMING AND DATA REVIEW

Programming of analysis datasets, tables, figures and listings will be ongoing during the data management of the study. Outputs for the DSMB will be reviewed, but no formal quality control (QC) will take place. Blind outputs may be reviewed by Abivax before DBL.

When the final data is considered clean, key listings (to be agreed) will be run and distributed to the study team for review. A blind DRM will be held to discuss the outcome of this review, the imputations for the primary endpoint and the protocol deviations. Once all data issues have been resolved and the analysis populations approved, the database will be locked. The final run of outputs and QC will then take place.

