3.5 SAMPLE SIZE CONSIDERATIONS

The primary efficacy endpoint is the rate of subjects responding to treatment. This response rate will be compared in subjects who received ABX464 or placebo by likelihood ratio chi-squared test. For the sample size assessment, the following assumptions will be made:

Response rate for ABX464: 0.6

• Response rate for placebo: 0.2

According to literature, the response rate for ABX464 treated subjects is expected to be between 50% and 75% while that in the placebo group is assumed to be approximately 10% to 20%.

The Type I error is defined to be one-sided 10% significance level, and the group allocation rate is 2:1 (ABX464/ placebo). If the above assumptions and these definitions hold true with a sample size of 30 subjects receiving ABX464 or placebo in a ratio of 2:1, then the study has 81% power to show a difference in response rate between the treatment groups. Power was computed using the normal approximation method. A 2:1 randomisation ratio was chosen to gain more clinical experience with ABX464 in this indication, despite the inevitable loss of power. The actual loss of power with the above assumptions is 4%.

Subjects who terminate the study prematurely will be considered failures, therefore no adjustment for dropouts is needed.

The primary safety endpoint is the rate of all treatment emergent adverse events. The above sample size is sufficient to detect an increase in general treatment emergent adverse event rate from 10% to 50% with 86% power by likelihood ratio chi-squared test at a one-sided 10% significance level.

If approximately 20 subjects receive ABX464, the study has 88% chance to detect at least I specific treatment emergent adverse event if the underlying rate of occurrence is 1:10. When the underlying rate of occurrence is around 1:20 the sample size of 20 subjects is sufficient to observe at least I such an event with a probability of 64% in the active treatment group.

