10 STATISTICAL METHODS

10.1 GENERAL PRINCIPLES

All statistical methods will be based on the International Conference on Harmonisation (ICH) E9 document "Statistical Principles for Clinical Trials".

Data will be summarised by treatment group. A total column showing all patients will be included for baseline and safety summaries. Where appropriate, data will also be summarised by visit with summaries for each visit attended as scheduled and an additional summary for final (last scheduled visit or early withdrawal). The format of the summaries is defined in the shells at the end of this document.

In summary and analysis tables of continuous variables, standard descriptive statistics (N, mean, standard deviation [SD], median, minimum and maximum) will be presented. Quartiles, least squares mean (LS mean), standard error (SE) and 95% confidence interval (CI) will be presented in the statistical analysis outputs as appropriate. For PK summaries, arithmetic mean (AM), geometric mean (GM) and coefficient of variation (%CV) will be used to summarise the data. The minimum and maximum statistics will be presented in summary tables to the same number of significant figures as the original data. The mean/AM, median, LS mean, GM, CI, SD and SE will be presented to one more significant than the original data.

For numeric data which includes non-numeric values (e.g. PK data reported as below limit of quantification [BLQ] or lab results reported as < 10 or > 100) the following principles will be applied when summarising the data:

- BLQ will be replaced with a value that is ½ of the lower limit of quantification (LLQ)
- Results reported as < x will be treated in the same way as BLQ with LLQ=x
- Otherwise AM, GM, SD, Cl and %CV will not be calculated
- Whenever meaningful, minimum, median and maximum will be presented based on the reported data (e.g. minimum = <10, median = 20, maximum = >100)

In summary tables of categorical variables, the number of non-missing observations by category will be presented with percentages. The number of missing observations will also be presented when non-zero. Unless otherwise specified, the denominator for each percentage will be the number of non-missing observations within the column. All percentages will be presented to one decimal place.

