10.2 Missing Data

There will be no imputation of missing data in this study.

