11.3 EFFICACY ANALYSES

Treatment comparisons will be ABX464 vs placebo. The main analysis set for the efficacy analyses will be the PP, and the primary analysis will be repeated for the FAS Set.

Subjects who prematurely terminate the study will be considered failures.

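### The SAP's ban on imputation conflicts with counting early terminators as failures, a Day 56 completer without a Week 8 score drops out of the remission rate, and the failure rule cannot act in the per-protocol set

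*SAP*

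**What the plan says.** Five parts of the SAP bear on a missing Week 8 remission outcome.

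- **10.2 Missing Data:** "There will be no imputation of missing data in this study".
- **9.4 Programming and Data Review:** the blinded review meeting before database lock will discuss "the imputations for the primary endpoint and the protocol deviations". No method is given.
- **11.3 Efficacy Analyses:** "Subjects who prematurely terminate the study will be considered failures". SAP 3.5 and Protocol 9.2 and 9.4 carry the same rule, and both sample-size sections use it to justify making no allowance for dropout.
- **10.1 General Principles:** unless something else is specified, "the denominator for each percentage will be the number of non-missing observations within the column". Counts of missing observations are shown when not zero.
- **6.3 Per Protocol Set:** membership has two conditions beyond the FAS, no major deviation and completion to Day 56.

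SAP 11.3 makes PP the main efficacy set, with the remission analysis repeated on the FAS. Protocol 9.2 places the efficacy analysis in the FAS, and SAP 6.1 assigns primary analyses to the FAS. The shell for Tables 14.2.1.1 (PP) and 14.2.1.2 (FAS) has N, Yes and No rows and no denominator footnote. Other shells, such as Table 14.1.2, do state their denominator.

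**The concern.** Classifying a subject with no Week 8 score as a failure assigns a value to a missing outcome. Section 10.2 forbids that, 11.3 requires it for some subjects, and 9.4 implies that something of the kind is still to be settled. A programmer cannot follow all three literally.

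Two kinds of subject are affected. One is the early terminator. The other is the subject who attends to Day 56 but has no usable Total Mayo Score. That score needs the endoscopy sub-score, and Protocol 5.3.6 has each video checked for quality before central reading, so an unreadable Week 8 video is a realistic case. Such a subject has not terminated prematurely.

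Remission is a secondary endpoint, but it is the primary efficacy endpoint, is formally tested, and drives the sample size. With 20 and 10 subjects per arm, one or two subjects in or out of the denominator matter.

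**Working it through.** **1. The plan's own figure.** Inputs from SAP 3.5 and 3.1: "Response rate for ABX464: 0.6"; "Response rate for placebo: 0.2"; one-sided 10% level; 20 and 10 subjects.

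- Pooled rate = (20×0.6 + 10×0.2)/30 = 0.4667
- Null SE = √[0.4667×0.5333×(1/20 + 1/10)] = 0.1932
- Alternative SE = √[0.6×0.4/20 + 0.2×0.8/10] = 0.1673
- Power = Φ[(0.4 − 1.2816×0.1932)/0.1673] = Φ(0.911) = 81.9%

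The stated figure is 81%, so it reproduces.

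**2. Which rule reaches which subject.**

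| Subject | FAS table 14.2.1.2 | PP table 14.2.1.1 |
|---|---|---|
| Early terminator | Failure under 11.3, if 11.3 overrides 10.1 and 10.2 | Not in the set (6.3) |
| Day 56 completer, no evaluable Week 8 Total Mayo Score | 11.3 does not apply; no value under 10.2; out of the denominator under 10.1 | The same, if kept in PP |

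The failure rule therefore acts in one cell of four, and there only by giving the specific section priority over the general ones.

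**3. Effect on the comparison.** The documents give no dropout or missing-data rate, so the counts below are assumptions: 8 remitters on ABX464 and 2 on placebo. The test is the one-sided likelihood ratio test without strata (the planned test is stratified): G = 2 Σ O·ln(O/E) over the four cells, p = 1 − Φ(√G).

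For 8/20 vs 2/10 the expected remitters are 6.667 and 3.333 and the expected non-remitters 13.333 and 6.667. G = 2[8 ln(8/6.667) + 12 ln(12/13.333) + 2 ln(2/3.333) + 8 ln(8/6.667)] = 1.262; √G = 1.124; p = 0.131.

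| Missing subjects removed | Rates | G | p |
|---|---|---|---|
| None (all counted as non-remitters) | 8/20 = 40% vs 2/10 = 20% | 1.262 | 0.131 |
| 2 ABX464 | 8/18 = 44% vs 2/10 = 20% | 1.760 | 0.092 |
| 4 ABX464 | 8/16 = 50% vs 2/10 = 20% | 2.458 | 0.058 |
| 2 ABX464, 1 placebo | 8/18 = 44% vs 2/9 = 22% | 1.329 | 0.124 |
| 1 placebo | 8/20 = 40% vs 2/9 = 22% | 0.908 | 0.170 |

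**4. The no-allowance argument.** Assume that 0.6 and 0.2 are completer rates, dropout is equal in both arms, and nobody is replaced. The formula in step 1 gives:

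| Dropout | Dropouts removed, as in PP | Dropouts as failures, as in FAS |
|---|---|---|
| 10% | 27 subjects, 78.5% power | 30 subjects, 75.7% power |
| 20% | 24 subjects, 74.5% power | 30 subjects, 69.0% power |
| 30% | 21 subjects, 69.9% power | 30 subjects, 61.9% power |

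In PP the number analysed falls below 30, so the reason given for making no allowance does not apply to the main analysis.

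**The case against.** The strongest reply is that the specific rule governs the general one. Section 10.1 applies only where nothing else is specified, and 11.3 does specify. An early terminator classed as a failure has a non-missing value, No, and stays in the FAS denominator. That stands. A reader might infer that early terminators disappear from the FAS table, but the documents do not support that as more than a literal reading of 10.2.

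A reader might also count 9.4 as a further, competing rule. It is an agenda item without a method, for a blinded meeting, and the randomisation list is loaded only after lock (SAP 9.3), so a decision there could not follow the results by arm. The formal primary endpoint is TEAEs (SAP 4.1), and SAP 11.4.1 has defaults for incomplete adverse-event data to which 9.4 may refer. That also stands. On either reading, though, 9.4 does not fit 10.2, and blinding does not supply a pre-specified rule.

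Three further replies limit the size:

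- Missing counts will be displayed, so exclusions would be visible.
- Removing subjects with missing scores raises either arm's rate whenever that arm has remitters. It need not favour ABX464: the last row in step 3 moves against it.
- Subjects who leave for non-drug-related reasons are replaced (Protocol 7.2, SAP 3.6), which would offset part of the loss in step 4.

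Finally, a per-protocol set excludes non-completers by design. That alone is no fault. The difficulty is that SAP 11.3 makes this set the main analysis, while the protocol and the sample-size argument rely on the failure rule.

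None of this supplies a rule for the Day 56 completer without an evaluable score.

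**Conclusion.** The point holds in three parts. First, 10.2 cannot stand as written beside the failure rule or beside 9.4. Second, a Day 56 completer without an evaluable Week 8 Total Mayo Score is left out of the rate and the test. Third, the failure rule never acts in the PP table, so the justification for no dropout allowance does not hold for the main efficacy analysis.

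Two missing ABX464 subjects are enough in the example to cross the one-sided 10% level (0.131 to 0.092); with equal proportions missing the result stays above it (0.124). These figures rest on assumed counts and an unstratified test. They show that the rule can decide the result, not that it will or in which direction.

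A reader might infer from step 4 that PP costs power relative to the failure rule. On those assumptions it does not: counting dropouts as failures gives the lower power. The failure rule makes an allowance unnecessary only if 0.6 and 0.2 already count dropouts as failures. The argument for the FAS rule is consistency with the protocol and a fixed denominator, not power.

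This should be corrected. It affects a secondary but formally tested endpoint.

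**What to change.** 1. In SAP 10.2 and 11.3.1, state that for the binary Week 8 endpoints any FAS subject without an evaluable Week 8 score, for whatever reason, is a non-responder; that the denominator is all FAS subjects in the arm, including any withdrawn subject who was replaced; and that no other imputation is made for these endpoints.
2. Remove the 9.4 reference to imputations or align it with this rule. If it concerns adverse events, point it to 11.4.1.
3. Add the denominator as a footnote to Table 14.2.1.2.
4. Make the FAS table the main remission analysis, as in Protocol 9.2, and show PP and observed-case results as sensitivity analyses. This means edits to 11.3, 11.3.1 and the table list. Tables 14.2.2.4 and 14.2.2.5 are listed for PP only, so they need FAS versions if the rule is to cover endoscopic remission, mucosal healing and clinical response.

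The cost is SAP text, one footnote and a few repeated tables, with no new data, visits or subjects. The reported remission rate may be slightly lower.

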10 STATISTICAL METHODS

10.1 GENERAL PRINCIPLES

All statistical methods will be based on the International Conference on Harmonisation (ICH) E9 document "Statistical Principles for Clinical Trials".

Data will be summarised by treatment group. A total column showing all patients will be included for baseline and safety summaries. Where appropriate, data will also be summarised by visit with summaries for each visit attended as scheduled and an additional summary for final (last scheduled visit or early withdrawal). The format of the summaries is defined in the shells at the end of this document.

In summary and analysis tables of continuous variables, standard descriptive statistics (N, mean, standard deviation [SD], median, minimum and maximum) will be presented. Quartiles, least squares mean (LS mean), standard error (SE) and 95% confidence interval (CI) will be presented in the statistical analysis outputs as appropriate. For PK summaries, arithmetic mean (AM), geometric mean (GM) and coefficient of variation (%CV) will be used to summarise the data. The minimum and maximum statistics will be presented in summary tables to the same number of significant figures as the original data. The mean/AM, median, LS mean, GM, CI, SD and SE will be presented to one more significant than the original data.

For numeric data which includes non-numeric values (e.g. PK data reported as below limit of quantification [BLQ] or lab results reported as < 10 or > 100) the following principles will be applied when summarising the data:

- BLQ will be replaced with a value that is ½ of the lower limit of quantification (LLQ)
- Results reported as < x will be treated in the same way as BLQ with LLQ=x
- Otherwise AM, GM, SD, Cl and %CV will not be calculated
- Whenever meaningful, minimum, median and maximum will be presented based on the reported data (e.g. minimum = <10, median = 20, maximum = >100)

In summary tables of categorical variables, the number of non-missing observations by category will be presented with percentages. The number of missing observations will also be presented when non-zero. Unless otherwise specified, the denominator for each percentage will be the number of non-missing observations within the column. All percentages will be presented to one decimal place.

If changes in severity for the same TEAE have been reported separately but with the same adverse event (AE) number, they will be collapsed to a single AE with maximum severity for the summary tables, but listed as reported.

Classifications of medical history, concomitant medication and adverse events will be sorted alphabetically within the summary tables.

If any laboratory assessments are repeated at the same visit, the result from the repeat assessment will be used in summaries. Both values will be listed.

Data collected on the eCRF will be presented within data listings. The data listings will be sorted by treatment group, country, centre number, patient number and visit/week/day. Treatment group will be as allocated (randomised). If any patients receive the wrong treatment this will be flagged in all listings. Visits outside the visit windows will be identified within the listings.

The date format for all output presentations will be 'ddMMMyyyy'.

All statistical analysis will be performed using SAS 9.3 or higher.

P-values will be rounded to four decimal places. P-values less than 0.0001 will be reported as <0.0001 in tables.

If any of the assumptions underlying the formal statistical methods proposed are violated during the analysis of the final data, alternative statistical methods will be used and any changes documented in the statistical methods section of the CSR, including the rationale for use.

10.2 Missing Data

There will be no imputation of missing data in this study.

10.3 POOLING OF SITES

Sites will be pooled for all analyses. There will be no adjustment for centre effect or treatment by centre interaction.

10.4 STATISTICAL ISSUES

There are no statistical issues.

11 STATISTICAL OUTPUT

General principles for layout of the statistical output are described in Section 10.1, including specification of the table columns, and these are illustrated for each unique table in the table shells in Section 15. For clarity and brevity in this document the phrase "by treatment group" is understood for all summaries and is not included within the text of this section.

The study analysis will be performed following database lock upon the completion of the last patient or upon its early discontinuation whichever occurs first.

11.1 PATIENT DISPOSITION

A patient is considered to be a baseline failure if the patient signs the informed consent but withdraws before the screening visit. Reasons for exclusion will be recorded for patients who do not enter the study and presented in a data listing.

A patient who does not fulfil the randomisation criteria will be considered as a screen failure.

A summary of the number of screened patients, baseline failures, screening failures and reasons for screening failure will be produced for all enrolled patients (*Table 14.1.1*).

The number (%) of patients who complete or withdraw from the study and the main reason for withdrawal will be summarised for all randomised patients (*Table 14.1.2*).

The patient disposition table (Table 14.1.3) will summarise the following data for all randomised patients:

- The number (%) of patients in the FAS
- The number (%) of patients in the safety set
- The number (%) of patients in the PP set

A data listing presenting the eligibility for the analysis sets for each patient will also be presented.

Protocol deviations will be reviewed and classed as major or minor during the blind DRM. A listing of all patients with protocol deviations will be presented.

11.2 PATIENT CHARACTERISTICS AT BASELINE

11.2.1 Demographic and Baseline Characteristics

Age will be calculated using Date of Birth (DOB) and date of informed consent and presented as age at last birthday as an integer.

Body mass index (BMI) is the patient's body weight in kilograms divided by the square of the patient's height in metres.

Age, gender, race, baseline height, baseline weight and BMI will be summarised using the FAS (*Table 14.1.4*).

11.2.2 Medical History and Current Medical Conditions

All conditions will be coded using the version of the Medical Dictionary for Regulatory Activities (MedDRA) defined in the Data Management Plan (DMP). Past medical/surgical history (conditions that stopped prior to or at the screening visit) and current medical conditions (classified as 'ongoing') will be summarised by system organ class (SOC) and preferred term (PT). The number (%) of patients reporting each condition will be presented using the FAS (*Table 14.1.5.1* and *14.1.5.2*).

